5.5 Pre-study Test Participants

Up to 6 participants will be analysed to optimize study design and procedures. The participants will partake in the three arms, including the optimization periods. Data from these participants will not be included in the final study analysis.

6 Intervention Visits Procedures

6.1 24-hour Intervention Procedures

For patient's convenience, the patient will be given an option to sleep on site one night prior to the intervention, with research staff available on site. Study procedures, however, will start in the morning of the scheduled intervention.

Identical procedures will be used during the three 24-hour inpatient visits. Each 24-hour intervention visit will include three meals (8:00, 12:00, and 17:00), evening snack (21:00), and an overnight stay. Meals and snacks will be standardized between visits for the same participant. Participants will be admitted at the research facility around 7:00 and will be discharged between 8:00 and 8:30 the next morning. For the intervention visit with regular insulin and pramlintide, the visit will start at 7:40am.

Insulin (fast-acting or regular) infusion will be changed manually every 10 minutes based on the control algorithm that relies on the glucose sensor readings. The basal-bolus pramlintide will be infused using the second pump with a fixed ratio to insulin delivery (i.e., will also be changed manually every 10 minutes). Participants will be blinded to the glucose sensor measurements. Venous blood samples will be sampled for the measurement of plasma glucose, plasma insulin, plasma glucagon, and plasma amylin.

The detailed study procedures description is as follows.

[figure not shown]

Figure 2 Study intervention procedures

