5.1 Recruitment

Potential participants will be recruited at the McGill University Health Centre - Adult Diabetes Clinic, Montréal, Canada. A total of 28 participants will be enrolled in the study. The study will be conducted at the Centre for Innovative Medicine (CIM) at McGill University Health Centre Research Institute,

Montréal, Canada. Participants showing interest in participation will have the study fully explained to them and will be offered the opportunity to ask questions. Interested participants that meet basic eligibility criteria will be scheduled for the admission visit.

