6.3 Blood Sampling

6.3.1 Blood sampling schedule

Blood samples (2 ml) will be obtained according to the following schedule:

8:00, 8:10, 8:20, 8:30, 8:40, 9:00, 9:20, 9:40, 10:00, 10:30, 11:00, 11:30, 12:00, 12:10, 12:20, 12:30, 12:40, 13:00, 13:20, 13:40, 14:00, 14:30, 15:00, 15:30, 16:00, 16:30, 17:00, 17:10, 17:20, 17:30, 17:40, 18:00, 18:20, 18:40, 19:00, 19:30, 20:00, 20:30, 21:00, 21:30, 22:00, 22:30, 23:00, 23:30, 0:00, 0:30, 1:00, 1:30, 2:00, 2:30, 3:00, 3:30, 4:00, 4:30, 5:00, 5:30, 6:00, 6:30, 7:00, 7:30, 8:00.

Blood samples (2ml) will be obtained according to the following schedule for the intervention with regular insulin and pramlintide:

7:40, 7:50, 8:00, 8:10, 8:20, 8:40, 9:00, 9:20, 9:40, 10:00, 10:30, 11:00, 11:30, 11:40, 11:50, 12:00, 12:10, 12:20, 12:40, 13:00, 13:20, 13:40, 14:00, 14:30, 15:00, 15:30, 16:00, 16:30, 16:40, 16:50, 17:00, 17:10, 17:20, 17:40, 18:00, 18:20, 18:40, 19:00, 19:30, 20:00, 20:30, 21:00, 21:30, 22:00, 22:30, 23:00, 23:30, 0:00, 0:30, 1:00, 1:30, 2:00, 2:30, 3:00, 3:30, 4:00, 4:30, 5:00, 5:30, 6:00, 6:30, 7:00, 7:30, 8:00.

In addition, if plasma glucose is < 3.3 mmol/L, extra samples may be taken each 10-15 minutes until plasma glucose rises again above 3.3 mmol/L, then the pre-defined sampling schedule will be re-followed.

Any situations that delay or disable the nurse from taking the plasma sample on time will be recorded in patient's Case Report File, but will not be considered a protocol deviation. Additionally, any extra plasma samples will be recorded in patient's Case Report File, but will not be considered a protocol deviation.

In the event that the plasma glucose is unavailable due to IV issues or for other reasons, the study will proceed based on sensor glucose values.

To reduce costs, only a sub-group of participants (n=14) may be analyzed to measure plasma insulin, plasma glucagon and plasma amylin concentrations. Samples for the other 14 participants may be analyzed if deemed necessary by the investigators based on the availability of funds. Samples that are measured will be chosen in a scientifically appropriate manner.

Plasma glucose will be measured in real time using YSI2300 STAT Plus Analyser (Yellow Springs, Ohio, USA). Plasma insulin, amylin and glucagon will be measured by immunoassay (Millipore, Billerica, MA, USA).

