7.1.2 Secondary endpoints and comparisons

1. Percentage of time of glucose levels spent in target range, comparing fast-acting insulin-plus-pramlintide closed-loop delivery vs. regular insulin-plus-pramlintide closed-loop delivery.
2. Percentage of time (8:00-8:00) of glucose levels spent:
 - a.* between 3.9 and 7.8 mmol/L; *b.* between 3.9 and 10 mmol/L; *c.* below 3.9 mmol/L; *d.* below 3.3 mmol/L; *e.* below 2.8 mmol/L; *f.* above 7.8 mmol/L; *g.* above 10 mmol/L; *h.* above 13.9; *i.* above 16.7 mmol/L.
3. Percentage of overnight time (23:00-8:00) of glucose levels:
 - a.* between 3.9 and 7.8 mmol/L; *b.* between 3.9 and 10 mmol/L; *c.* below 3.9 mmol/L; *d.* below 3.3 mmol/L; *e.* below 2.8 mmol/L; *f.* above 7.8 mmol/L; *g.* above 10 mmol/L; *h.* above 13.9; *i.* above 16.7 mmol/L.
4. Standard deviation of glucose levels as a measure of glucose variability.
5. Total insulin delivery.
6. Total pramlintide delivery.
7. Mean glucose level during: *a.* the overall study period; *b.* overnight period.
8. Mean insulin concentration.
9. Mean glucagon concentration.
10. Mean amylin concentration.
11. Number of participants experiencing hypoglycemia requiring oral treatment during: *a.* the overall study period; *b.* the night.
12. Gastrointestinal symptoms during the treatment optimization (i.e., the minimum 10 days prior to the 24-hour closed-loop visits) and during the 24-hour closed-loop visits.

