10.1 Adverse Events (AE)

An adverse event is any untoward medical occurrence or unfavorable and unintended sign in a subject administered a pharmaceutical product, biologic (at any dose), or medical device, whether or not considered related to the use of that product. This includes the onset of new illness and the exacerbation of pre-existing conditions.

Additionally, any event that is associated with or observed in conjunction with a product overdose (whether accidental or intentional) or a product abuse and/or withdrawal is also considered an adverse event. Adverse event is considered also malfunction or lack of function of any software or hardware part of the artificial pancreas system which results in symptoms.

The onset and end dates, severity and relationship (causality) to study drug/device/procedure will be recorded for each adverse event. Any action (treatment) or outcome (e.g., hospitalization, discontinuation of therapy, etc.) will also be recorded for each AE.

Adverse events will be collected from the time of signing the informed consent until the subject finishes his/her participation in the study, including non-interventional days.

After the last per-protocol contact the investigator does not need to actively monitor patients for AEs. However, if the investigator becomes aware of SAEs that occurred after the last per protocol contact and if there is suspected causal relationship to the study intervention, the SAEs will be reported by the investigator.

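### The blanket exclusion of pre-study participants' data in Section 5.5 also removes their tolerability data from the final results; it should apply to efficacy endpoints only

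*Combined protocol and SAP*

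**What the plan says.** Section 5.5 sets the purpose and ceiling of the pre-study phase: "Up to 6 participants will be analysed to optimize study design and procedures". On exposure it says: "The participants will partake in the three arms, including the optimization periods". On the use of their results it says: "Data from these participants will not be included in the final study analysis". The section makes no exception for safety or tolerability and describes no separate report for these participants.

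Two planned secondary endpoints in Section 7.1.2 concern tolerability and safety. Endpoint 11 is "Number of participants experiencing hypoglycemia requiring oral treatment during" the whole study period and the night. Endpoint 12 is "Gastrointestinal symptoms during the treatment optimization (i.e., the minimum 10 days prior to the 24-hour closed-loop visits) and during the 24-hour closed-loop visits".

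Section 10.1 applies to all subjects without exception: "Adverse events will be collected from the time of signing the informed consent until the subject finishes his/her participation in the study". Section 10.4 adds serious-event reporting to the ethics committee and Health Canada, and follow-up of all events.

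On numbers, Section 5.1 says "A total of 28 participants will be enrolled in the study". Section 6.3.1 describes a hormone-assay subgroup of 14 and then says "Samples for the other 14 participants may be analyzed if deemed necessary".

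**The concern.** Leaving pilot participants out of the efficacy analysis is good practice, because the design and procedures may be adjusted after them. That reason does not carry over to tolerability. These people receive the same drug, by the same route, for the same two optimization periods and two inpatient visits as everyone else on pramlintide. Whether a person had nausea, vomiting or treated hypoglycemia while exposed is information about the intervention, even if some procedures later changed.

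As written, the rule makes no such distinction. A reader of the final results would see tolerability for the main-study participants only, and would not learn what happened in up to six further people with full exposure. In a trial of this size, six people are a sizeable part of the safety experience.

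**Working it through.** **Step 1. What the exclusion reaches.** Setting the sections side by side for a pre-study participant:

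- Adverse events: collected (10.1), with serious events reported and all events followed up (10.4). The exclusion in 5.5 concerns the final analysis, so it leaves these duties intact.
- Treated hypoglycemia and gastrointestinal symptoms (7.1.2, endpoints 11 and 12): these are analysis endpoints, so 5.5 removes them.
- Adverse-event summary: Section 7 plans none for anyone. If one is produced as part of the final analysis, 5.5 keeps these participants out of it.

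**Step 2. Number of people.** The plan's own figure is 28 (5.1). Section 6.3.1 accounts for it as 14 + 14 = 28 main-study participants, which points to the pre-study participants being additional. Under 7.2, only people who complete at least one insulin-plus-pramlintide visit count toward the recruitment goal, so all 28 are exposed to pramlintide. With the maximum of six:

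- Exposed: 28 + 6 = 34.
- Share left out: 6/34 = 17.6%.

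**Step 3. Amount of exposure.** Each pre-study participant has two pramlintide arms. Each arm has an optimization period of at least 10 days with a target of 14 (4.1, 8.1.1), plus one 24-hour visit.

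- At the minimum: 6 × 2 × (10 + 1) = 132 participant-days.
- At the target: 6 × 2 × (14 + 1) = 180 participant-days.

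**Step 4. Effect on what the trial can rule out.** For an event seen in nobody, the one-sided 95% upper bound on per-person risk is 1 − 0.05^(1/n).

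- n = 28: 1 − 0.05^(1/28) = 10.1%.
- n = 34: 1 − 0.05^(1/34) = 8.4%.

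The difference is 1.7 percentage points. The figure for 34 pools pre-study and main-study participants and so assumes that the risk is the same in both.

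**Step 5. Chance that something is actually left out.** The documents give no event rate, so this step uses assumed per-person risks. The chance that at least one of six people has the event is 1 − (1 − p)^6.

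- p = 2%: 11%.
- p = 5%: 26%.
- p = 10%: 47%.

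**The case against.** The strongest reply is that the safety of these participants is already covered. Their adverse events are collected, and serious ones are reported and followed up. That is correct, and it means that a reader who infers that their safety data go unrecorded or unreported to authorities has read too much into 5.5. What remains is narrower: endpoints 11 and 12, and any adverse-event summary, would not include them.

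A second reply is that procedures may change after the pilot, so adding its events to the main study would mix different conditions. This has force. It argues for a separate column or listing, but not for leaving the data out.

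Three stronger readings are tempting, and the documents do not support them.

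- **That status could be settled after the glucose result is known.** The number is only capped, and no time of designation is stated. But the section calls these people pre-study participants and excludes them unconditionally, which implies labelling in advance. Nothing ties the number to time in range. Any inflated false-positive rate would presuppose conduct that the plan does not describe.
- **That the six sit inside the 28 and use up the drop-out allowance.** The 14 plus 14 in Section 6.3.1 point the other way, and 7.2 reserves the margin above 22 for drop-outs, technical problems and uncertainty in the power calculation. The sample size is not in question.
- **That tolerability would be biased downward because pilots have more problems.** This is conceivable, but nothing in the documents shows it. The point rests on lost information and not on a known direction of bias.

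**Conclusion.** The point holds for safety and tolerability reporting. Section 5.5 states a rule, and the rule is wider than its purpose needs. It leaves up to 6 of 34 exposed people (17.6%), and about 132 to 180 pramlintide participant-days, out of the final tolerability results.

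These figures assume that all six places are used, that the six are additional to the 28, and that they go through both pramlintide arms in full. The plan says that they take part in the arms, not that they complete them. With fewer pre-study participants the loss shrinks, to nothing if there are none. The 14-day figure is a target and not a maximum. The denominator of 34 ignores people replaced under 7.2, who may also have been exposed.

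The primary comparison is unaffected. The change is worth making because it is cheap and gives a complete account of exposure, not because the trial's conclusions depend on it.

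**What to change.** Amend Section 5.5 so that the exclusion applies to efficacy endpoints only. State there, naming endpoints 11 and 12 so that neither is taken for an efficacy endpoint, that adverse events, gastrointestinal symptoms and treated hypoglycemia will be reported for everyone exposed. Show pre-study participants in their own column or listing, since procedures may change after the pilot.

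As minor wording, state in 5.5 that pre-study participants are designated before their first intervention visit, and in 5.1 that they are additional to the 28.

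The cost is a few sentences and one extra safety table. No further participants, procedures or data collection are needed, and the sample size stays as it is.

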6.1.1 Initial procedures (7:00-8:00)

- Participants will be admitted at the MUHC Research Institute Centre for Innovative Medicine (CIM) around 7:00.
- Participant's weight will be obtained.
- For women for childbearing potential, a pregnancy test will be performed
 - Women 50 years or older with an absence of menstrual bleeding for the past year will not be required to take the pregnancy test.
 - Women that underwent hysterectomy will not be required to take the pregnancy test.
- Revision of inclusion and exclusion criteria
- Revision of the patient's medication
- A cannula will be inserted into the antecubital or hand vein for blood sampling purposes.
- Participants will be asked to calibrate the glucose sensor using their capillary glucose level as measured by their meter.
- Presence of gastrointestinal symptoms (nausea, vomiting, bloating, and heart burn) will be assessed in the fasting state.
- The closed-loop study will begin at 7:40 (regular insulin) or 8:00 (rapid insulin).

6.1.2 Procedures related to Breakfast (8:00)

At 8:00, a mixed meal will be served containing 30g – 60g of carbohydrates. The carbohydrate content will be entered at the onset of the meal. Participants will have a choice to personalize the content of their meal from a menu of two main options. Study participants will consume the same meal at each

visit. Presence of gastrointestinal symptoms (nausea, vomiting, bloating, and heart burn) will be assessed in the post-prandial period.

6.1.3 Procedures related to Lunch (12:00)

At 12:00, a mixed meal will be served containing 50g – 80g of carbohydrates. The carbohydrate content will be entered at the onset of the meal. Participants will have a choice to personalize the content of their meal from a menu of four main options. Study participants will consume the same meal at each visit. Presence of gastrointestinal symptoms (nausea, vomiting, bloating, and heart burn) will be assessed in the post-prandial period.

6.1.4 Procedures related to Dinner (17:00)

At 17:00, a mixed meal will be served containing 70g – 100g of carbohydrates. The carbohydrate content will be entered at the onset of the meal. Participants will have a choice to personalize the content of their meal from a menu of four main options. Study participants will consume the same meal at each visit. Presence of gastrointestinal symptoms (nausea, vomiting, bloating, and heart burn) will be assessed in the post-prandial period.

6.1.5 Night procedures (21:00-8:00)

A 20g – 40g carbohydrate bedtime snack will be given at 21:00. The carbohydrate content will be entered at the onset of the meal. Participants will have a choice to personalize the content of their meal from a menu of 6 options. Study participants will consume the same snack at each visit. Presence of gastrointestinal symptoms (nausea, vomiting, bloating, and heart burn) will be assessed in the post-prandial period.

6.1.1 Discharge procedure (8:00 to 8:30 next morning)

Participants will be discharged between 8:00 and 8:30 the next morning from the inpatient admission. If patient's plasma or capillary glucose at discharge is below 5mmol/L, the patient will be offered a snack (oral carbohydrates 10-40 gCHO).

6.1.2 Procedures related to Activity

Throughout the 24-hour intervention, participants will be allowed to perform light activities such as walking, and play card, board, and video games. Participants will be encouraged to walk at least 30 min per day. If the participant's walk, the same activity should be performed at the three intervention visits.

6.2 Sensor Measurement

The algorithm requires to be updated with the current sensor measurement every 10 minutes from the start of the study until the end of the study. While the aim is to strictly follow the schedule, any situations that delay or disable the research staff from taking the sensor measurement and/or updating the pump settings on time will be recorded in patient's Case Report File, but will not be considered a protocol deviation.

6.3 Blood Sampling

6.3.1 Blood sampling schedule

Blood samples (2 ml) will be obtained according to the following schedule:

8:00, 8:10, 8:20, 8:30, 8:40, 9:00, 9:20, 9:40, 10:00, 10:30, 11:00, 11:30, 12:00, 12:10, 12:20, 12:30, 12:40, 13:00, 13:20, 13:40, 14:00, 14:30, 15:00, 15:30, 16:00, 16:30, 17:00, 17:10, 17:20, 17:30, 17:40, 18:00, 18:20, 18:40, 19:00, 19:30, 20:00, 20:30, 21:00, 21:30, 22:00, 22:30, 23:00, 23:30, 0:00, 0:30, 1:00, 1:30, 2:00, 2:30, 3:00, 3:30, 4:00, 4:30, 5:00, 5:30, 6:00, 6:30, 7:00, 7:30, 8:00.

Blood samples (2ml) will be obtained according to the following schedule for the intervention with regular insulin and pramlintide:

7:40, 7:50, 8:00, 8:10, 8:20, 8:40, 9:00, 9:20, 9:40, 10:00, 10:30, 11:00, 11:30, 11:40, 11:50, 12:00, 12:10, 12:20, 12:40, 13:00, 13:20, 13:40, 14:00, 14:30, 15:00, 15:30, 16:00, 16:30, 16:40, 16:50, 17:00, 17:10, 17:20, 17:40, 18:00, 18:20, 18:40, 19:00, 19:30, 20:00, 20:30, 21:00, 21:30, 22:00, 22:30, 23:00, 23:30, 0:00, 0:30, 1:00, 1:30, 2:00, 2:30, 3:00, 3:30, 4:00, 4:30, 5:00, 5:30, 6:00, 6:30, 7:00, 7:30, 8:00.

In addition, if plasma glucose is < 3.3 mmol/L, extra samples may be taken each 10-15 minutes until plasma glucose rises again above 3.3 mmol/L, then the pre-defined sampling schedule will be re-followed.

Any situations that delay or disable the nurse from taking the plasma sample on time will be recorded in patient's Case Report File, but will not be considered a protocol deviation. Additionally, any extra plasma samples will be recorded in patient's Case Report File, but will not be considered a protocol deviation.

In the event that the plasma glucose is unavailable due to IV issues or for other reasons, the study will proceed based on sensor glucose values.

To reduce costs, only a sub-group of participants (n=14) may be analyzed to measure plasma insulin, plasma glucagon and plasma amylin concentrations. Samples for the other 14 participants may be analyzed if deemed necessary by the investigators based on the availability of funds. Samples that are measured will be chosen in a scientifically appropriate manner.

Plasma glucose will be measured in real time using YSI2300 STAT Plus Analyser (Yellow Springs, Ohio, USA). Plasma insulin, amylin and glucagon will be measured by immunoassay (Millipore, Billerica, MA, USA).

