4.1 Trial Design

This study is a randomized, three-way, crossover trial to compare the efficacy of **i)** fast-acting insulin-plus-pramlintide closed-loop delivery, **ii)** regular insulin-plus-pramlintide closed-loop delivery, and **iii)** fast-acting insulin-alone closed-loop delivery in regulating glucose levels over a period of 24 hours in a study on adults in inpatient settings. Insulin (fast-acting and regular) and pramlintide are given with fixed ratio (6 µg of pramlintide for each unit of insulin).

Before each 24-hour intervention visit, the participant's insulin therapy (basal rates and insulin-to-carbohydrate ratios) will be optimized for a minimum of 10 days, with a target of 14 days. If a participant is randomized to either rapid or regular insulin-plus-pramlintide arms, pramlintide will be infused using a second pump at a fixed ratio for a minimum of 10 days, and insulin therapy will be optimized. Regular insulin will replace participant's usual insulin and will be initiated for a minimum of 10 days, and insulin therapy will be optimized.

There will be a wash-out period of 0 to 42 days between the three intervention arms (termination of 24-hr intervention and start of next optimization period).

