7.1 Study Endpoints

7.1.1 Primary comparisons

Percentage of time of glucose levels spent in target range (defined to be between 3.9 and 10.0 mmol/L). The following comparisons will be done:

- i) Fast-acting insulin-plus-pramlintide closed-loop delivery vs. fast-acting insulin-alone closed-loop delivery;
- ii) Regular insulin-plus-pramlintide closed-loop delivery vs. fast-acting insulin-alone closed-loop delivery.

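### Does the separate plasma sampling grid of the regular-insulin visit bias its glucose comparisons, given that section 7.1 names no glucose source or weighting rule?

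*Combined protocol and SAP*

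**What the plan says.** Section 7.1.1 defines the primary endpoint as "Percentage of time of glucose levels spent in target range (defined to be between 3.9 and 10.0 mmol/L", without a glucose source, clock window or weighting rule. Section 7.1.2, item 2, lists the same range ("between 3.9 and 10 mmol/L") under "Percentage of time (8:00-8:00) of glucose levels spent", and section 4.1 describes the comparison as one "in regulating glucose levels over a period of 24 hours". Further secondary endpoints are "Standard deviation of glucose levels as a measure of glucose variability", "Mean glucose level during" the overall and overnight periods, and "Mean insulin concentration" with its glucagon and amylin counterparts. None of these has an averaging rule, and section 7.4 adds none.

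Two glucose records exist. The sensor is read every 10 minutes in every arm (section 6.2). Plasma is drawn on a fixed schedule (section 6.3.1), which is separate for one arm: "Blood samples (2ml) will be obtained according to the following schedule for the intervention with regular insulin and pramlintide". That visit starts at 7:40 instead of 8:00. In any arm, extra samples may be drawn every 10 to 15 minutes while plasma glucose is below 3.3 mmol/L. Sections 6.4.1 and 6.4.2 make plasma the default for treatment decisions, but not for endpoints.

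**The concern.** Primary comparison ii and secondary comparison 1 set the regular-insulin arm against an arm sampled on a different grid. The regular-insulin grid has more samples just before meals, when glucose is usually lower, and fewer at 30 minutes after meals, when it is often rising. If samples were counted or averaged as collected, the schedule would be confounded with treatment. A false gain of a few points would matter against a planned effect of 7 points. The wording of the mean and SD endpoints does not rule out a plain average of whatever was drawn. Primary comparison i is not at risk on the scheduled samples, because both its arms use the 61-time grid. Nor are the scheduled overnight samples, which are the same 19 times in all arms.

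**Working it through.** **1. The plan's own figures.** Counting the two lists in section 6.3.1 gives 61 and 64 times, as section 6.3.2 states; 58 are common. The regular-insulin grid adds 7:40, 7:50, 11:40, 11:50, 16:40 and 16:50, and omits 8:30, 12:30 and 17:30. Samples in the 2 hours after the three meals: 24 of 61 against 21 of 64. Samples from 30 minutes before a meal up to the meal: 5 of 61 against 11 of 64. The sample size in section 7.2 also reproduces: a paired t-test with difference 7, SD 10 and two-sided alpha 0.025 needs n = 22 (power 80.0%).

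**2. If samples were counted.** Suppose 75% of the 61 samples are in range (45.75). Let p be the share in range among the six added samples and q the share among the three dropped ones. The shift is (45.75 + 6p − 3q)/64 − 0.75.
- p = 0.90, q = 0.65: 49.2/64 − 0.75 = +1.9 points.
- p = 0.65, q = 0.90: 46.95/64 − 0.75 = −1.6 points.

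The documents give no glucose profile, so larger checks rest on simulated curves (baseline plus meal rises). Nine scenarios matched section 1 (70–75% in range, 20–25% high). In these, counting shifts time in range by about +1 to +5 points and mean glucose by −0.13 to −0.41 mmol/L (−0.04 to −0.34 within 8:00–8:00). SD shifts by −0.15 to +0.02. In a looser set of 38 scenarios, matched on time in range only, 8 reverse sign (−0.9 to −2.1 points).

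With SD 10, a false shift of 1, 2 or 3 points would raise the 2.5% error rate to about 4%, 9% or 18% at n = 22, and to 4%, 11% or 23% at n = 28.

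**3. If time is measured.** Within 8:00–8:00 the grids differ inside five intervals only. Three run from 20 to 40 minutes after a meal (3 × 20 = 60 minutes) and two are the half-hours before lunch and dinner (2 × 30 = 60 minutes). Each interval has the same endpoints on both grids. Extra points inside an interval add no time, so a difference can come only from interpolation error within 120 of 1,440 minutes.

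A sharp-edged example has glucose out of range from 30 to 120 minutes after each meal in both arms (true time in range 1,170/1,440 = 81.2%).
- Counting: 43/61 = 70.5% against 49/64 = 76.6%, a gap of 6.1 points.
- Crude time-weighting, with each in-range or out-of-range reading carried half-way to its neighbours. Out of range per meal is 5 + 90 + 15 = 110 minutes on the fast-acting grid and 10 + 80 + 15 = 105 on the regular grid. Time in range is (1,440 − 330)/1,440 = 77.1% against (1,440 − 315)/1,440 = 78.1%, a gap of 1.0.
- Linear interpolation of glucose on smooth curves: 0.01 to 0.08 points in the matched scenarios, and 0.0 to 0.6 in a separate set with other peak times and baselines.

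If the sensor record is used, the interval is the same in every arm. Starting at 7:40 instead of 8:00 moves the result by 0.05 to 0.28 points.

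**4. Extra low samples.** An assumed 60-minute overnight low is 60/1,440 = 4.2% of the day. Counted, it is 2/61 = 3.3% on schedule, 4/63 = 6.3% with 15-minute extras and 6/65 = 9.2% with 10-minute extras. The rule applies in every arm, and time-weighting stops the extra samples from inflating the total.

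**The case for a change.** The strongest case for a change is that the derivation of a primary endpoint should not be left to inference. Two glucose records are available and the plan does not choose between them. It gives no endpoint rule for missing plasma. A plain mean or SD of the collected samples is a literal reading of section 7.1.2. Cutting to 8:00–8:00 does not cure a naive count: the sharp-edged example still gives 47/62 = 75.8%, which is 5.3 points too high. A few lines of text would settle all of this at no cost in samples or visits.

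The gap in the text is real, and the counts behind it are correct. What does not stand is the step from gap to bias. The primary endpoint is expressed in time, and its window can be inferred from item 2 of section 7.1.2 and the 24 hours in section 4.1. The choice between plasma and sensor remains open, but on neither does the arm-specific grid matter once time is measured. For mean glucose and SD the wording gives less protection. These are secondary endpoints, however, with shifts of at most about 0.4 mmol/L in the mean and 0.15 in SD, and time-weighting is ordinary practice for unequally spaced samples. For the hormones no size has been shown. Section 6.3.1 limits assays to a possible subgroup of 14 and leaves the choice of samples to scientific judgement, so the full arm-specific grid need not be what is averaged.

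**Conclusion.** No change to the plan follows. The grids do differ by arm and section 7.1 is silent on source and weighting, but the bias appears only if plasma samples are counted or averaged as collected, which the plan does not prescribe. Read as time, primary comparison ii moves by 0.0 to 0.6 points with linear interpolation and by about 0.3 at most on the sensor record, against a planned effect of 7. These are maxima over assumed smooth curves, not strict bounds; a deliberately crude calculation on a sharp-edged profile gives 1.0. Under naive counting the shift would be about +1 to +5 points on curves matched to section 1, and its size and sign would depend on a profile that the documents do not give. Writing the rule down would mostly record what a competent analyst would do anyway.
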